6.1.2.2 GIRERD Questionnaire

The GIRERD Questionnaire is used to evaluate treatment compliance, and is made up of 6 yes or no questions, such that:

- *If the patient responds “no” to all questions, he is considered as a good complier.*
- *If the patient responds “yes” once or twice, he is considered as a minor complier.*
- *If the patient responds “yes” three times or more, he is considered as a non-complier.*

The GIRERD Questionnaire is completed at all visits (Inclusion visit, V1, V2, V3, V4, V5, V6 and any additional visits in the case of discontinuation of Tofacitinib).

6.2 SAFETY ENDPOINTS

The reporting of safety data will be in accordance with Pfizer Data Standards. In addition, endpoints involving the occurrence of the following adverse events of special interest will also be investigated:

1. Herpes Zoster.
2. Serious Infections.

A serious infection is any infection (viral, bacterial, and fungal) that requires hospitalization for treatment or requires parenteral antimicrobial therapy or meets other criteria that require it to be classified as a serious adverse event (results in death, is life-threatening, causes substantial disability or incapacity, or results in a congenital anomaly or birth defect).

The number of AE's adjusted by a patients duration on the study, where duration of time on the study is calculated as per Section **Error! Reference source not found.**, will be calculated as:

$$\frac{\text{Number of Adverse Events}}{\text{Duration of time on study}}$$

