6.1.1.2 Secondary Endpoints

There are multiple secondary endpoints in this study, described in the following subsections.

For the secondary endpoints which consider duration of time on the study, duration of time on the study will be calculated as:

$$\text{Date of Last Visit} - \text{Date of Baseline Visit} + 1$$

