8.1.7 Area Under the Curve

For PCS total score, the 3 domains of PCS and the 5 domains of the CSQ, the Area under the curve (AUC), for each score over time, will be calculated from baseline to last follow-up visit.

As patients will not be on the study for the same length of time, AUC will then be adjusted by the duration which each patient is in the trial, where duration is calculated as per Section **Error! Reference source not found..**

Thus, adjusted AUC will be calculated as:

$$\frac{\text{Area under the Curve}}{\text{Duration of time on study}}$$

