8.2.6 Secondary Analyses

All secondary analyses will use the FAS. Secondary analyses will consider Tofacitinib Total as the treatment group. Summaries of secondary endpoints will be presented for Tofacitinib total, Tofacitinib as monotherapy and Tofacitinib as combination, using the treatment labels seen in Section 2.3.

Each endpoint will apply the specific rules for missing data as described in Section 7 but if there are missing data points after this, no missing data methods will be used to impute data for the secondary analyses.

All the analyses described hereafter in this section will be performed on all assessments collected before permanent Tofacitinib discontinuation (On-Treatment Analysis). In addition, analyses described in sub-sections 8.2.6.2, 8.2.6.3, 8.2.6.4 and 8.2.6.5 will be re-run on all available data including retrieved dropout data (Analysis on All Available Data).

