Further summaries will be produced to investigate the relationship between behavioural strategies and the adverse event (AE) groups Herpes Zoster and Serious Infections. Serious infections are as defined in Section 6.2. The summaries will be presented separately for the two groups, and are as follows:

- The baseline behavioural strategies (PCS total score, PCS (3 domains) and CSQ (5 domains)) statistics, summarized as per Section **Error! Reference source not found.**, will be presented for patients who experienced each AE of interest (Herpes Zoster/Serious Infection) and for patients who did not experience the AE of interest.
- The last behavioural strategies (PCS total score, PCS (3 domains) and CSQ (5 domains)) statistics, summarized as per Section **Error! Reference source not found.**, for measurements prior to the first occurrence of the AE of interest (for patients who experienced the AE of interest) will be presented. The last behavioural strategies measurements in the study for patients who did not experience the AE of interest will also be presented.
- Correlation between the number of AE's of interest and behavioural strategies (PCS total score, PCS (3 domains) and CSQ (5 domains)) at baseline will be

examined using the methods described in Section **Error! Reference source not found..**

- Correlation between the number of AE's of interest and the last behavioural strategies (PCS total score, PCS (3 domains) and CSQ (5 domains)) prior to the first occurrence of an AE will be examined using the methods described in Section **Error! Reference source not found..**
- The correlation between the adjusted number of AE's (see Section 6.2) and the adjusted AUC for PCS and CSQ (see Section **Error! Reference source not found..**) will be calculated and presented, as per Section **Error! Reference source not found..** This will be done for:
 - PCS total score.
 - The 3 domains of the PCS.
 - The 5 domains of the CSQ.
- The change in behavioural strategies (PCS total score, PCS (3 domains) and CSQ (5 domains)) before and after start of the first occurrence of the AE of interest will be presented for the subset of patients who experience the AE of interest, summarized as per Section **Error! Reference source not found..**

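### The SAP gives conflicting windows for the PCS/CSQ area under the curve (8.2.6 against 8.1.7) and no window for the AE count (6.2), so the adjusted AUC–AE correlation is not defined

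*SAP*

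**What the plan says.** - **Data rule.** SAP 8.2.6 says that the analyses in that section are to be "performed on all assessments collected before permanent Tofacitinib discontinuation (On-Treatment Analysis". It then states that "analyses described in sub-sections 8.2.6.2, 8.2.6.3, 8.2.6.4 and 8.2.6.5 will be re-run on all available data". Section 8.2.6.1 is not in that list.
- **The analysis concerned.** It sits in SAP 8.2.6.1: "The correlation between the adjusted number of AE's (see Section 6.2) and the adjusted AUC for PCS and CSQ". It covers nine scores: PCS total, three PCS domains and five CSQ domains.
- **AUC.** In SAP 8.1.7 the AUC, "for each score over time, will be calculated from baseline to last follow-up visit". The same section adds: "AUC will then be adjusted by the duration which each patient is in the trial".
- **AE count.** SAP 6.2 defines "The number of AE's adjusted by a patients duration on the study" as AEs divided by time on study. It gives no counting window.
- **Duration.** The cross-references in 6.2 and 8.1.7 do not resolve. The only definition is in SAP 6.1.1.2: "For the secondary endpoints which consider duration of time on the study, duration of time on the study will be calculated as" last visit minus baseline visit plus 1.
- **Follow-up.** SAP 2.2 keeps patients who stop tofacitinib in follow-up for the full 24 months.

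**The concern.** Dividing an AUC by its duration should return the patient's average score, so that patients observed for different lengths of time can be compared. That works only if both parts cover the same period. Under the on-treatment rule the AUC stops at discontinuation while the divisor runs to the last study visit. The result is then the average score multiplied by the fraction of follow-up spent on drug.

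If AEs are cut at discontinuation too, both correlated quantities carry that same fraction, and some association follows by construction. The protocol plans on 50% drug survival, so about half the cohort could be affected. No multiplicity adjustment is planned. Because 8.1.7 and 8.2.6 conflict, two programmers following the SAP could obtain values several-fold apart for the same patient, with no all-data version of this correlation to reveal it.

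**Working it through.** **Plan's own figure (Protocol 9.5).** Variables entering the model: 50 × 0.3 = 15. Events: 15 × 10 = 150. Patients: 150 / 0.50 = 300. This reproduces, and it supplies the 50% share of stoppers used below. The documents state no figure for the AUC or AE ratios.

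**Shrinkage if 8.2.6 governs.** Take a constant score s, last on-treatment assessment on day d, and last visit on day 731 (target day of Visit 6, SAP Table 9). The AUC is s × (d − 1). The divisor is 731 − 1 + 1 = 731. With s = 20:

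| Last on-treatment day | AUC | AUC / 731 | Too low by | Divisor ending on day d |
|---|---|---|---|---|
| 30 | 580 | 0.79 | 25-fold | 19.33 |
| 91 | 1,800 | 2.46 | 8.1-fold | 19.78 |
| 183 | 3,640 | 4.98 | 4.0-fold | 19.89 |
| 365 | 7,280 | 9.96 | 2.0-fold | 19.95 |
| 548 | 10,940 | 14.97 | 1.3-fold | 19.96 |

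The small remaining gap from 20 in the last column comes from the +1 in the duration formula. Dividing by d − 1 gives exactly 20.

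**How many stoppers, and by how much.** Assume a constant stopping hazard, 50% stopped by day 731 and all stoppers followed. The share of stoppers with on-drug fraction at or below f is (1 − 2^(−f)) / 0.5.
- f = 0.5 (at least 2-fold): 59%.
- f = 0.25 (at least 4-fold): 32%.
- f = 0.125 (at least 8-fold): 17%.
- The median fraction solves 2^(−f) = 0.75, so f = 0.415, a 2.4-fold reduction.

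**If 8.1.7 governs.** A constant score of 20 gives 20 × 730 / 731 = 19.97 for anyone followed to day 731. There is no shrinkage, but scores after stopping enter an analysis that 8.2.6 labels on-treatment.

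**Correlation when none exists.** Simulation of 300 patients with exponential stopping (50% by day 731), PCS normal with mean 20 and SD 10 clipped to 0–52, PCS independent of AEs and of stopping, and Poisson AEs. There were 1,000 runs per scenario (400 where AEs cause stopping). The AE rates, PCS distribution and share of stoppers followed are assumptions; none is in the documents. Cells show mean Spearman rho and the share of runs with two-sided p < 0.05.

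| Scenario (study-time divisor) | 0.03 per patient-year | 0.06 | 0.5 | 1.5 |
|---|---|---|---|---|
| AUC and AEs both cut at stopping, all stoppers followed | 0.07 (21%) | 0.10 (39%) | 0.29 (99.7%) | 0.44 (100%) |
| Same, half of stoppers followed | 0.03 (7%) | 0.05 (11%) | 0.14 (72%) | 0.24 (99%) |
| AUC cut, AEs over whole study, AEs unrelated to stopping, all followed | 0.00 (6%) | 0.00 (5%) | 0.00 (4%) | 0.00 (6%) |
| AUC cut, AEs over whole study, half of on-treatment AEs cause stopping | not run | −0.11 (45%) | −0.25 (99.5%) | not run |

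With no stopper followed, rho is 0.00 to 0.01 (5–6%). With matched windows and all stoppers followed the problem disappears: all on-treatment gives rho 0.00 to 0.01 (4–6%), and all on-study gives about 0.00 (3–6%).

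**The case against.** The strongest reply is that 8.1.7 is the specific definition and 8.2.6 only a general rule. On 8.1.7 alone, AUC and divisor both end at the last visit and nothing is wrong. The same holds if the last visit is taken from the on-treatment data. This is a fair reading, and it rules out calling the formula a demonstrated error. It does not settle the matter: neither section says which prevails, and 8.2.6.1 is absent from the all-available-data re-run, which is where the 8.1.7 reading would belong.

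Second, nothing limits the AE count in 6.2 to on-treatment events. The rule in 8.2.6 speaks of assessments. AEs are collected at every follow-up visit, and SAP 8.2.2.1 lists events after cessation. Whole-study AEs over study time is a coherent rate. This stands: 6.2 is incomplete, not wrong in itself.

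Third, the paragraph in 8.2.6.1 concerns Herpes Zoster and Serious Infections, for which low rates are the natural assumption and the spurious rho is small. This largely stands, although the bullet itself does not repeat the restriction to AEs of interest, so a count of all AEs is also possible.

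Fourth, the effect needs follow-up after stopping, and Protocol 9.1.5 and 10.3 allow early withdrawal. Also, SAP section 4 states no formal hypotheses, and 8.1.2 plans coefficients without mentioning tests. The rejection rates above therefore show only what attached p-values would do.

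**Conclusion.** The windows for AUC, AE count and duration are not reconciled. If 8.2.6 governs, the adjusted AUC is understated for every stopper who stays in follow-up: 4-fold for a stop at day 183, with a median of 2.4-fold among stoppers under constant-hazard stopping and complete follow-up. If 8.1.7 governs, the ratio is sound but not on-treatment.

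A reader might infer that the plan shrinks AE rates as well and so builds in a false positive correlation. The documents do not support that. It needs 8.2.6 to override 8.1.7, AE truncation that no section states, and follow-up of stoppers. Its size rests on assumed AE rates, and its sign can reverse when AEs are counted over the whole study and cause stopping.

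Nor does the adjusted AUC under 8.2.6 mostly measure time on drug. In 500 simulated cohorts with all stoppers followed it correlated 0.68 with drug time and 0.64 with true PCS, about equally.

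The consequence is limited to an exploratory correlation. The primary Cox analysis and the three behavioural Cox models do not use these ratios.

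**What to change.** Reconcile SAP 6.1.1.2, 6.2, 8.1.7 and 8.2.6 so that AUC, AE count and denominator share one window. Either choice removes the artefact:

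- **All on-treatment.** Divide the AUC to the last on-treatment assessment by that date minus the baseline assessment date. Divide on-treatment AEs by time on drug plus any stated lag. SAP 8.2.2.1 already uses 28 days for treatment emergence; the lag must be the same in count and denominator.
- **All on-study.** Take AUC, AE count and duration to the last visit, and add this correlation to the all-available-data analysis in 8.2.6.

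Also state in 8.2.6.1 whether the count is all AEs or only the two AEs of interest, and repair the duration cross-references.

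Cost: two or three SAP lines and no new data. The on-treatment option makes rates noisier for short exposures.

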7 HANDLING OF MISSING VALUES

Missing data indicators method (see Section 7.1) will be used for the primary analysis and sensitivity analyses, where specified. If there are more than 10% missing data in baseline covariates then a sensitivity analysis using complete case analysis will also be produced. The sensitivity analysis will check for bias using the missing data indicators methods, which is understood to exhibit bias in the occurrence of a large proportion of missing data. (1) If a large difference is seen between the primary analysis and the sensitivity analysis then other missing data methods may be used.

Furthermore, random survival forests methods will be produced as an additional sensitivity analysis to complement the primary model. Missing data methods for random survival forests are described below in Section 7.3.

Missing data methods for questionnaire data are described in Sections 7.4 to Section 0.

7.1 MISSING DATA INDICATORS

Missing data indicators is not a form of imputing, and is used to check if data is missing at random (2). For each factor with missing data in the primary analysis, an indicator variable will be created as

$$\begin{aligned} 1 &= \text{Missing} \\ 0 &= \text{Otherwise} \end{aligned}$$

The indicator variables will be added to the multivariate Cox PH model, following backwards selection, described in Section 8.1.1.1 Cox Proportional Hazards. The model will have a missing data indicator for each variable in the model with missing data.

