First, the effect of each factor on drug survival will be tested with a univariate Cox model. Thus, the hazard-ratios calculated are called “raw”. They will be presented with their 95% confidence interval and their associated p-value. Then, all potential factors for which the p-value resulting from univariate analysis is strictly less than 10% will be included in a multivariate Cox model. Predictive factors and their interactions will be chosen using a backward (step-down) selection. Predictive factors chosen will be those which have a p-value < 5%. In the case of a significant interaction, all individual components of the interaction will be “forced” in the model, whether they are statistically significant or not. The adjusted hazards-ratios thus obtained will be presented with their 95% confidence interval and their associated p-value.

Missing data will be managed using a method based on missing data indicators^(50, 51). This method is not a method of imputation of missing data. A fixed value will be assigned to missing observations, and a dummy variable (1/0) will be added to the multivariate model in order to indicate if the value of this variable is missing or not. If more than 10% of the patients have missing baseline covariates, a complete case analysis will also be performed as a sensitivity analysis. Additional methods for handling missing data may also be used. Further details will be provided in the statistical analysis plan as appropriate.

Secondary analyses

The impact of behavioural strategies (catastrophisation and coping) on Tofacitinib drug survival will be evaluated in patients suffering from RA. A Cox proportional hazards model will be used with the 5 dimensions in the coping questionnaire and the catastrophisation score collected at the baseline visit included as independent variables.

In a second phase and in a similar manner, a Cox model will be used to estimate the impact of the adaptive strategies under treatment. Therefore, the last evaluation available before discontinuation of treatment (or the last visit if a patient does not permanently discontinue treatment) and the change between this latter evaluation and the baseline value will be taken into account in separate models.

The correlation between behavioural strategies and effectiveness will be studied with Pearson's or Spearman's coefficient according to the nature of variables compared.

Interim analysis

Interim descriptive analyses will be conducted annually.

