1.2 AMENDMENTS FROM THE PROTOCOL

The handling of visit windows has been amended in the SAP compared to the protocol. The Protocol states that:

In order to collect comparable study data, visits 2 to 9 occurring +/- 14 days of the scheduled visit date will be used for data analysis.

As the visits will be scheduled according to clinical practice there are likely to be many visits outside of the windows defined in the protocol. To ensure the primary analysis incorporates all visits at which a patient might experience a treatment escalation all visits will be included for the primary analysis, based on the windowing in [Table 9](#) of Section [11.1](#).

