8.1.1 Analysis of Time to Event Data

8.1.1.1 Cox Proportional Hazards

Cox proportional hazards (PH) models will be used to analyse time to event data, where the event of interest is duration of Tofacitinib drug survival described in Section **Error! Reference source not found.** If a patient is not recorded as having permanently discontinued Tofacitinib, which is the event of interest, then they will have their time of follow-up censored at the date of their last visit.

For the primary analysis, univariate Cox PH models will be created for all of the potential predictive factors, see [Figure 2](#) in Section [8.2.3](#), that is a separate Cox PH model will be created for each factor. If the variable significantly impacts Tofacitinib drug survival at the 10% level then the factor will be put forward into a multivariate model.

Once the univariate model selection is complete, backwards selection will be used to remove factors from the multivariate model which do not have a significant p value at the 5% level. The covariate with the highest p value will be removed in turn until all factors have a p value less than 0.05. If a significant interaction is found then the individual factors of this interaction will be kept in the model, regardless of their p value. A significant interaction is tested for between all variables in the multivariate model.

Furthermore, for the primary analysis a table showing all of the 95% confidence intervals and p values for the “raw” hazard ratios coming from the univariate models will be created. This will be for all of the factors in [Figure 2](#), regardless of whether they’re included in the multivariate model.

For the secondary analysis, a multivariate Cox PH model will be created including the scores from the 5 domains of the CSQ at baseline and the total PCS score at baseline included as covariates.

A further two Cox PH models will be produced for the secondary analysis, for CSQ and PCS: the first including the last evaluation available before discontinuation (or last visit if

patient does not discontinue during the study) and the second including change from baseline to the last recorded measurement.

The SAS procedure PROC PHREG will be used to fit any Cox PH models and check the assumption of proportional hazards. If the assumption of proportional hazards is violated then alternative models will be considered.

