8.2.3 Primary Analyses

The primary endpoint, duration of Tofacitinib drug survival, will be analysed using the FAS and the methods described in Section 8.1.1.1 Cox Proportional Hazards. The Tofacitinib drug survival tables will present a single Tofacitinib Total column, using the treatment label seen in Section 2.3. A Kaplan-Meier plot will present the survival function for Tofacitinib Total group. As a comparison, a second KM plot will present the

survival functions for both Tofacitinib as Monotherapy and Tofacitinib as Combination groups. The treatment labels seen in Section 2.3 will be used.

The list of potential predictive factors to include in the model for the primary analysis is seen in [Figure 2](#). Note: the factors seen in Figure 2 are all baseline predictors. Where SF-12 is considered within [Figure 2](#), the 8 health domains as well as PCS_{SF12} and MCS will each be considered as potential predictive factors. As PCS_{SF12} and MCS are linear combinations of the 8 health domains, collinearities are anticipated, however considering all of them as potential predictors will allow us to investigate which domains contribute the most to PCS_{SF12} and/or MCS. If necessary, transitional models will be investigated including separately component summary measures (PCS_{SF12} and MCS) and the 8 health domains.

Figure 2: Potential predictive factors of drug survival

In the event of missing data, see Section 7.1. Missing data methods will be performed on the final multivariate Cox PH model, and not for the individual univariate models.

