8.2.9 Summary of Analyses

Table 8 Summary of Main Analyses

Outcome	Analysis Set	Supports Protocol Objective Number	Subgroups	Statistical Method	Covariates/ Strata	Missing Data
Time to discontinuation of Tofacitinib	Full Analysis Set (FAS)	1	None	Cox PH model	Univariate model selection, followed by backwards selection on the variables in Figure 2 .	Missing data indicators
Sensitivity Analysis – Only to be used in the event of >10% missing data: Time to discontinuation of Tofacitinib	FAS	1 – Sensitivity Analysis	None	Cox PH model	Univariate model selection, followed by backwards selection on the variables in Figure 2 .	Complete Case Analysis
Sensitivity Analysis: Time to discontinuation of Tofacitinib	FAS	1 – Sensitivity Analysis	None	Random Survival Forests	Variables in Figure 2 , following methods seen in Section 8.1.1.2 Random Survival Forests .	Random Survival Forests missing data algorithm.
Sensitivity Analysis: Time to discontinuation of Tofacitinib	Month 3 Analysis Set	1 – Sensitivity Analysis	None	Cox PH model	Univariate model selection, followed by backwards selection on the variables in Figure 2 and Das28-4 CRP at Baseline.	Missing data indicators
Sensitivity Analysis: Time to discontinuation of Tofacitinib	Month 3 Analysis Set	1 – Sensitivity Analysis	None	Random Survival Forests	Variables in Figure 2 and DAS28-4 CRP at Month 3, following the methods seen in Section 8.1.1.2 Random Survival Forests .	Random Survival Forests missing data algorithm.
Time to discontinuation of Tofacitinib	FAS	2	None	Cox PH model	Baseline CSQ and baseline PCS	No missing data methods used.
Time to discontinuation of Tofacitinib	FAS	2	None	Cox PH model	Last recorded CSQ and PCS before discontinuation.	No missing data methods used.
Time to discontinuation of Tofacitinib	FAS	2	None	Cox PH model	Change from baseline to last recorded CSQ and PCS before discontinuation.	No missing data methods used.

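### As written, the SAP brings in missing-data indicators only after backward selection and leaves out the protocol's fixed value, so primary predictors are selected on complete cases and the indicators cannot be estimated

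*SAP*

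**What the plan says.** Protocol 9.7 describes a two-part method: "A fixed value will be assigned to missing observations, and a dummy variable (1/0) will be added to the multivariate model". It does not say whether this happens before, during or after backward selection.

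SAP 7.1 defines only the 1/0 indicator and gives its timing: "The indicator variables will be added to the multivariate Cox PH model, following backwards selection". SAP 8.2.3 says the same in other words: "Missing data methods will be performed on the final multivariate Cox PH model, and not for the individual univariate models". No section of the SAP assigns a value to the missing covariate itself.

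SAP 8.1.1.1 describes the selection, "The covariate with the highest p value will be removed in turn until all factors have a p value less than 0.05", and names no missing-data rule for those steps.

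SAP 7 says that indicators "will be used for the primary analysis and sensitivity analyses, where specified". In Table 8 (SAP 8.2.9), the primary row gives the procedure as "Univariate model selection, followed by backwards selection on the variables in" Figure 2, and its missing-data column reads "Missing data indicators". The next row lists the same selection under complete-case analysis, as a sensitivity analysis to be run only if more than 10% of data are missing.

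SAP 1.2 lists one change from the protocol: "The handling of visit windows has been amended in the SAP compared to the protocol". It does not mention missing data.

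**The concern.** The primary objective is to identify which factors predict drug survival, so the selection is itself the result. If selection runs on a reduced sample, a true factor may be removed for lack of events, and an indicator added afterwards cannot bring it back.

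Protocol 9.5 sizes the study at 10 events for each factor expected to pass the screen, with no reserve. Gaps in baseline factors are to be expected: protocol 9.2 requires no additional examination, and protocol 9.3 collects only what is in the medical record.

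The planned safeguard is also weak. SAP 7 relies on the complete-case analysis to reveal bias from the indicator method. If the primary backward steps already run on complete cases, the two analyses share most of their selection path and may agree for that reason alone.

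**Working it through.** **1. The plan's own figure.** Inputs from protocol 9.5: 50 candidate factors, 30% passing the screen, 10 events per factor, 50% drug survival at 24 months.
- Factors: 50 × 0.3 = 15
- Events: 15 × 10 = 150
- Patients: 150 / 0.50 = 300

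This reproduces the protocol exactly.

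**2. What the rule does in a Cox fit.** A patient without a value for some covariate cannot contribute to the partial likelihood. With neither a fixed value nor imputation, each backward step uses only patients complete on the factors then in the model. In the final fit the excluded patients are exactly those whose indicator equals 1, so the indicator is 0 for everyone retained.

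A simulated data set (300 patients, 150 events, 15 factors, 3% missing independently per factor) confirmed this. The 15-factor model kept 195 patients and 94 events, and every indicator was 0 in all of them. A one-factor final model kept 294 patients, again with the indicator constant at 0. With a fixed value, all 300 patients and 150 events were used.

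**3. Events kept by a 15-factor starting model.** The missing rate m per factor is an assumption. Formulas: 150 × (1−m)^15 if gaps are independent, 150 × (1−m)^5 if they fall in five blocks, and 150 × (1−m) if they all coincide.

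| Pattern | m = 2% | m = 5% |
|---|---|---|
| Independent | 110.8 | 69.5 |
| Five blocks | 135.6 | 116.1 |
| Coinciding | 147.0 | 142.5 |

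Blocks are the more plausible pattern. Protocol 9.1.3 hands out the questionnaires together, and by SAP 8.2.3 the SF-12 alone supplies 10 candidates (8 domains plus 2 summaries).

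**4. Effect on selection at 5% missing.** Simulation of 600 runs per setting:
- 300 patients and 150 events
- 50 candidates in 10 blocks of 5, with correlation 0.5 within and 0.08 between blocks
- screen at p < 0.10 and backward elimination at p < 0.05
- 3 true factors with HR 1.3 per SD
- gaps completely at random; fixed value equal to the observed mean

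About 16 factors passed the screen. With full data a true factor was kept in 76.2% of runs. The Monte Carlo standard error is about 1 point.

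| Gaps | SAP rule, sample refreshed each step | SAP rule, sample fixed at start | Fixed value + indicator throughout |
|---|---|---|---|
| Blocks | 67.8% | 63.4% | 73.2% |
| Coinciding | 75.1% | 75.1% | 75.0% |
| Independent | 62.7% | 43.0% | 72.0% |

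Block case: 73.2 − 67.8 = 5.4 points and 73.2 − 63.4 = 9.8 points. Retention of null factors was 2.7% to 3.4% throughout.

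**5. Why no simulated 2% result is quoted.** The comparison arm dropped any indicator with fewer than 5 events or fewer than 5 non-events among the missing patients. At 2%, P(Bin(150, 0.02) ≥ 5) = 0.183, so both conditions hold with probability 0.183² = 0.033 and about 97% of indicators are dropped. That arm is then essentially mean substitution. At 5% the figures are 0.874² = 0.765, with about 24% dropped.

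**The case against.** **A reader might infer that Table 8 contradicts SAP 7.1.** It does not go that far. Table 8 is a summary that names a method and gives no timing, and the sentence in SAP 7 would also be true if indicators entered only the final model. There is a tension, because complete-case selection is shown as a separate sensitivity analysis, but no contradiction.

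**A reader might infer that the SAP has withdrawn the fixed value, or that its timing breaks the protocol.** The documents support neither. The SAP names the protocol's method and cites the same two missing-data sources, and nothing revokes the fixed value. Protocol 9.7 states no order, so late indicators are compatible with it. What stands is that the document to be programmed from omits a necessary part of the method and gives no value to use.

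**The word "following" in SAP 7.1 could mean in accordance with.** SAP 8.2.3 points to timing by naming the final model, although it may be contrasting only the multivariate with the univariate stage. If indicators are meant to apply throughout selection, the SAP should say so.

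**The sensitivity analyses are not worthless.** The complete-case screen may use a different sample from the primary screen, so its selected factors can differ. The random survival forests impute missing data and run whatever the extent of missingness. They remain an indirect check on Cox selection.

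**The loss may be small.** Protocol 9.8.2, 9.10.1 and 9.10.2 provide for queries, follow-up of omissions and exhaustive collection. The largest simulated losses need a sample fixed at the start, which SAP 8.1.1.1 does not say.

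**Indicators cost parameters.** Five shared indicators give 150 / 20 = 7.5 events per parameter. Complete cases with five blocks give 135.6 / 15 = 9.0 at 2% and 116.1 / 15 = 7.7 at 5%. The benefit of the change is therefore that patients are retained, not a better events-per-parameter ratio.

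**Conclusion.** The point holds as a defect in the written rule. Taken literally, SAP 7.1 and 8.2.3 run backward selection on complete cases and add indicators that cannot be estimated, while the main missing-data sensitivity analysis largely repeats the same selection.

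The structural part follows from the text and needs no assumption about missing rates. The size does. At an assumed 2% to 5% missing per factor, the starting model loses between 3 of 150 events (2%, coinciding gaps) and about 80 (5%, independent gaps). With block gaps the loss is about 14 to 34. At 5% missing, the chance of keeping a true factor falls by about 5 to 10 points with block gaps and not at all if gaps coincide. These figures also assume gaps completely at random, 15 factors entering and HR 1.3 per SD. Figure 2 is not shown, so the count of 50 candidates comes from protocol 9.5.

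This should be corrected before the primary model is run. Confidence in its practical effect is medium.

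**What to change.** In SAP 7.1 and 8.2.3:
- Restore the protocol's fixed value and state it, for example the observed mean or the reference category.
- Apply fixed value plus indicator from the start of multivariable backward selection, with each factor and its indicator entering and leaving together.
- Use one shared indicator for factors that are missing together, such as those from the same questionnaire.
- Where an indicator is dropped as too sparse, say that the factor is then handled by fixed-value substitution.
- Report the patients and events used at each step.
- Align both sections with Table 8, and list in SAP 1.2 any remaining departure from protocol 9.7.

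Only the fixed value restores the protocol. The timing is a clarification compatible with it, and the sharing and sparsity rules are additions.

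The cost is a few SAP lines and modest programming, with three statistical downsides:
- **Extra parameters.** Fifteen separate indicators give 30 parameters and 5 events per parameter; five shared ones give 20 and 7.5.
- **Sparse indicators.** With q = (1−m)^150, the chance that at least one of k indicators has missing patients but no event among them is 1 − (1 − q(1−q))^k. For k = 15 this is 94%, 51% and under 1% at 1%, 2% and 5% missing; for k = 5 it is 61%, 21% and under 1%.
- **Bias of the indicator method.** In simulation, a null factor correlated 0.6 with an incomplete predictor of HR 1.65 per SD showed HR 1.02, 1.04 and 1.08 at 5%, 10% and 20% missing.
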